### WP2: RCT

The RCT started in July 2020 and is still on going. In the initial FWO application the aim was to start the recruitment in April 2020 and to complete it by April 2021, with the final follow up in October 2021 (6 month after baseline assessment). A change to the timeline and sample size was necessary because of the low recruitment rate during the pandemic of Covid-19. The recruitment rate during the feasibility study before the pandemic (November 2019-February 2020) was 4-5 patients/month. The recruitment rate during the RCT was: 2.6 patients/month during the first year (July 2020-July 2021) and then 1.2 patient/month in the following 6 months (August 2021-January 2022). Fifty-four patients were included in the initial sample size calculation, estimating 15% of drop-out, power=90% and minimal clinically important difference (MCID)=8 points on the primary outcome SPADI. We planned to recruit patients until May 2022, aiming to 44 patients, with the last follow up measure in November 2022. Forty-four patients will still allow to have a well-powered study (85%) with MCID=10 points, which is considered in the range 8-13 points of the MCID in SPADI (Roy JS, MacDermid JC, Woodhouse LJ. Measuring shoulder function: a systematic review of four questionnaires. Arthritis Rheum. 2009;61(5):623-32). The extended time for data analysis in 2023 will allow the PhD student to conduct a thorough data analysis of objective and subjective data (see "Data analysis for 2nd term"). Status: 42 patients were recruited by the end of April 2022.

#### WP3: Data analysis

Data analysis 1st, 2nd US articles (WP3, 3.1 and 3.2): Status: data analysis completed. The time necessary for data analysis for the US measures was added to the timeline. *Main results*: inter-rater reliability was calculated in the reliability study performed in February 2020 with the US expert [name]. Inter-rater reliability varied largely from poor to good between two examiners with different US experience (novice VS expert examiner). However, since the only US examiner for the RCT is the PhD student, the data for the intra-rater reliability of the PhD student were considered relevant in order to proceed to the US measures in the RCT. The intra-rater reliability of the PhD

US measure	Intra-rater reliability, ICC (95%CI)							
AHD	0.97 (0.93-0.99)							
SSP	0.87 (0.71-0.94)							
AHD60	0.85 (0.69-0.93)							
AHD60w	<del>0.77 (0.52-0.90)</del>							
CHD0	0.93 (0.86; 0.97)							
LHB	0.90 (0.78; 0.96)							
SCP	0.92 (0.83; 0.97)							
CHD60	0.91 (0.81; 0.96)							
CHD60w	<del>0.88 (0.76; 0.95)</del>							
Table 2 - US measures. ICC: 2-way mixed model, absolute agreement (average measures). Abbreviations: AHD= Acromiohumeral Distance, AHD60= Acromiohumeral Distance at 60°; AHD60w= Acromiohumeral Distance at 60° with free weight; CHD= Coracohumeral Distance, CHD60= Coracohumeral Distance at 60°; CHD60w= Coracohumeral Distance at 60° with free weight; LHB= Long Head of Biceps tendon; SCP= Subscapularis tendon, SSP= Supraspinatus tendon.								

student can be found in Table 2. The ICC values for the PhD student are ranging from good to excellent (0.85-0.97). The measures with weights (AHD60w and CHD60w) were excluded in the final protocol in the RCT because of time limitations in the measurement protocol and also because the patients could not hold the weight assigned for the whole testing period.

The first manuscript resulting from this reliability phase was: "Subacromial space measured by ultrasound imaging in asymptomatic subjects and patients with subacromial shoulder pain: an inter-rater reliability study"; authors: [name], [name], [name], [name], [name], [name]; journal: Physiotherapy Theory and Practice (IF2020=2.28, Q3 Rehabilitation), **Manuscript 1**. The data analysis for the second manuscript has been completed and the manuscript will be submitted by June 2022 (see **Manuscript 2**).

Data analysis of feasibility study (WP3, 3.3): Status: data analysis completed. The time necessary for data analysis for the feasibility study was added to the timeline. The manuscript has been recently submitted (see **Manuscript 3**).

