Novelty/ relevance	Although the scapular control will be integrated in the exercises in both groups from the first session, we expect a greater improvement in G1 thanks to both increased muscle strength and regained self-efficacy in movement performance. Therefore, it is relevant to register how scapular dyskinesis is evolving during treatment in order to understand when and in which subgroups of patients it is contributing to symptoms of SSP.

OBJECTIVE 3	To investigate the effects of exercising into discomfort on changes in subacromial space (quantified as acromiohumeral distance AHD) and tendon structures measured by US imaging in SSP patients							
MethodsAnalysis of the secondary outcomes (subacromial space and tendon structure changes measured by US imaging) of the RCT conducted in objective 1								
Hypothesis	In both groups there will be an increase in the subacromial space and decrease in STT. These changes will be more evident in G1							
Novelty/ Relevance	The lack of understanding of tendon structural changes in "exercising into discomfort" in patients with SSP contributes to the inadequate management of this pathology. Information on such parameters will provide insights into the mechanisms behind this modality of exercise therapy during and after the end of the treatment. Moreover, this study aims to clarify the role of the subacromial space as a valuable indicator of SSP recovery. To the best of our knowledge, this is the first time that tendon structures are monitored during the treatment other than before and after rehabilitation (assessment at T2).							

OBJECTIVE 4 උ	To examine whether improvement in shoulder pain, function and quality of life is associated with changes in the subacromial space and tendon structures as measured by US imaging
Methods	Analysis of possible association between parameters measured by US (subacromial space, RC tendon thickness) and clinical symptoms (self-reported shoulder pain, questionnaires on functionality and quality of life) at T0, T1, T2, T3 in the RCT
Hypothesis	There will be a significant correlation between US imaging parameters and clinical symptoms

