#### Ultrasound measures

In May 2019 the US machine was bought with the budget of the doctoral grant. In August 2019 the PhD student followed a training on US imaging during a research stay of 4 days under the supervision of the US expert [name] at the partner University of Malaga (Task 1.4, WP1). In February 2020 this researcher came to Antwerp for a 2-week period to conduct an inter-reliability study on the US parameters previously decided and discussed during the research stay. This part of the project is currently in the phase of data analysis. This will allow to validate the skills of the PhD student as novice sonographer and to decide which US measures are valid and reliable to be part of the second phase (RCT, WP2). The US measures are described in WP2, under "Outcomes measures".

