# Outcome measures

All outcomes will be measured at baseline (T0) and 6 (T1), 12 (T2), 26 (T3) weeks and the assessors will be blinded to group allocation. The **primary outcome** is the **difference in mean change between groups from T0 to T1, T2 (12 weeks, end of the treatment), and T3 (26 weeks, follow-up)** in the patient self-reported outcome score **Shoulder Pain and Disability Index (SPADI)**. This questionnaire is a patient-reported outcome measure (PROM) with high test–retest reliability and construct validity  and is available and validated in Dutch .

Secondary outcomes are registered for each patient at the same time points as the primary outcome, except for the Global Perceived Effect Score, which will be assessed after 1st treatment and then at 6 and 12 weeks. The secondary outcomes are:

**Scapular dyskinesis:** The procedure we will use is based on the procedures described by Tate et al.  and Struyf et al. . Scapular position will be observed at rest and during active loaded and unloaded humeral motion in a frontal and sagittal plane. The effect of scapular correction will be tested by means of the modified scapular assistance test and scapular retraction test . Reduction of pain during these tests compared with non-assistance during the same tests confirms scapular involvement in the shoulder complaints.

**Subacromial space**: Acromiohumeral distance (AHD) is a US measurement used to quantify the subacromial space. It is defined as the shortest linear distance between the most inferior aspect of the acromion and the humeral head . AHD is measured at 0 and 60 degrees of active shoulder elevation in the scapular plane, following the procedure of measurement indicated by Navarro-Ledesma et al . It has already been used to evaluate different populations, such as healthy volunteers  and patients with shoulder pain .

**Tendon changes**: Tendon structural changes (limited to RC thickness and long biceps) will be evaluated using US device and following international guidelines . STT will be also computed as percentage of subacromial space, known as the occupation ratio (using the formula [(STT/AHD)\*100] .

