#### WP3: Data analysis

Data analysis of the RCT (WP3, 3.4 and 3.5): demographics and other objective measures (strength, range of motion, scapular dyskinesis, data from the US machine) will be processed already from June 2022, but the data concerning the randomization process of two groups will be unblinded only at the end of the trial in November 2022. Related manuscripts: see **Manuscript 4 and 5**. The end of the data analysis will be **Milestone 3**. *Status:* Milestone 3 has been delayed from Q2 2022 (initial FWO project) to Q4 2023. This delay is due to a decrease in patient recruitment caused by the pandemic of Covid-19. However, thanks to the extension of the FWO scholarship, there will be sufficient time to recruit all patients and to conduct a thorough data analysis for both objective and subjective measures.

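### The sole ultrasound examiner is masked to group allocation only, so the within-group changes of Objective 3 and the ultrasound-symptom correlations of Objective 4 are open to reader expectation

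*Combined protocol and SAP*

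**What the plan says.** **Who reads.** The renewal's progress section on WP3 (Data analysis) reports that "Inter-rater reliability varied largely from poor to good between two examiners", one a novice and one an expert. It then sets that result aside and relies on the student's intra-rater values in Table 2, "since the only US examiner for the RCT is the PhD student". In the application, the section on ultrasound measures says that the reliability study would "validate the skills of the PhD student as novice sonographer". The section on recruitment gives the second screening visit to the same student.

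**Masking.** Under Outcome measures, "the assessors will be blinded to group allocation". No passage describes masking to visit or symptoms, coded or random-order reading, a second reader in the RCT, or a lock on the ultrasound data.

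**Timing.** The renewal's plan for the second term says that the "data from the US machine) will be processed already from June 2022". Randomisation is unblinded, and the last follow-up takes place, in November 2022.

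**Questions asked.** The Objective 3 hypothesis is "In both groups there will be an increase in the subacromial space and decrease in STT", with larger changes expected in G1. Objective 4 expects ultrasound values and symptoms to be correlated. The application's analysis section models evolution within persons from baseline as well as differences between subjects.

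**The concern.** Masking to allocation answers one question: whether the reader could favour an arm. Two of the ultrasound questions do not depend on arm. The predicted change in both groups compares early with late scans, so it needs a reader who does not know which visit is being measured. The correlation with symptoms needs a reader who does not know how the shoulder feels. The plan states the expected direction of both results in advance, and neither question has an untreated group that would reveal a reader effect.

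The application itself says that ultrasound depends heavily on the operator. If a reader's expectation moved the measured distances slightly in the predicted direction, the trial could report a wider subacromial space, or a structural correlate of recovery, that came from the reading. The renewal plans a separate manuscript on the effect on the subacromial and subcoracoid spaces.

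**Working it through.** **1. The plan's own figure.** Table 2 lists seven retained measures: AHD 0.97, supraspinatus 0.87, AHD60 0.85, CHD0 0.93, long head of biceps 0.90, subscapularis 0.92 and CHD60 0.91. Their range is 0.85 to 0.97, as stated. The two measures with weights were dropped.

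These are average-measure ICCs, and the number of readings averaged (m) is not given. The single-measure equivalent is ICC/(m − (m−1)·ICC):
- Supraspinatus, m=2 (assumed): 0.87/1.13 = 0.77. With m=3: 0.87/1.26 = 0.69.
- AHD60, m=2: 0.85/1.15 = 0.74. With m=3: 0.85/1.30 = 0.65.

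Either way, the ICC describes how well one reader repeats a measurement within a short study in February 2020. It does not test whether a reading moves with knowledge of the visit or symptoms, or over a trial running from July 2020 to November 2022.

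**2. How many T3 scans are outstanding in June 2022.** Twenty-six weeks before 1 June 2022 is 1 December 2021. The renewal gives 2.6 patients a month for the first year from July 2020, then 1.2 a month from August 2021.
- First period counted as 12 months: 2.6×12 + 1.2×4 = 36.0 enrolled by then, so 44 − 36 = 8 outstanding.
- First period counted as 13 months: 2.6×13 + 1.2×4 = 38.6, so about 5 outstanding.

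Before dropout, 82% to 88% of patients have reached T3 when processing starts. Drift between reading batches is therefore a minor part of the point.

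**3. How small a reader effect would reach significance** (two-sided 0.05). The smallest observed mean shift, in SDs of the change score, is t(0.975, n−1)/√n. The critical correlation is t/√(n−2+t²), with t on n−2 degrees of freedom. After the planned 15% dropout, 44×0.85 gives about 37 patients.

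| n | Mean shift / SD of change | Critical r |
|---|---|---|
| 44 | 0.30 | 0.30 |
| 37 | 0.33 | 0.32 |
| 22 (one arm) | 0.44 | 0.42 |

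The documents give no SD for the change in AHD. If it lay between 0.6 and 1.5 mm (an assumption), the threshold would be 0.18 to 0.46 mm at n=44 and 0.27 to 0.67 mm in one arm.

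**4. False-positive rates under an assumed reader effect.** The within-person rows come from the noncentral t distribution with noncentrality s√n, where s is the shift in SDs and there is no true change. The correlation rows come from 20,000 simulated trials with no true association, where the reading moves by the stated number of SDs per SD of symptom change.

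| Test | 0.1 SD | 0.2 SD | 0.3 SD |
|---|---|---|---|
| Within-person change, n=44 | 10% | 25% | 49% |
| Within-person change, n=37 | 9% | 22% | 43% |
| Within-person change, n=22 | 7% | 15% | 27% |
| Correlation, n=44 | 10% | 25% | 48% |
| Correlation, n=37 | 9% | 21% | 41% |

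The same shift in both arms (0.3 or 0.5 SD, 22 per arm) leaves the between-group test at about 5%. This is the part that allocation masking protects.

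**The case against.** The strongest reply is that the gap is small and the plan has partly covered it. Only secondary outcomes are involved. SPADI is untouched, and the contrast between arms, which is the randomised part of Objective 3, is protected. The retained ICCs are good to excellent and were computed under absolute agreement, which penalises systematic differences between a reader's own measurements. The application also says that a standardised procedure and training can limit operator effects, and the renewal says that the student had acquired the necessary skills by February 2020. All of this stands, and it limits the weight of the point. It does not close the gap, because repeatability is not masking.

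A reader might infer more than the documents support:
- **That the examiner measures knowing the visit and symptoms.** The documents are silent. Baseline knowledge is plausible because the student screens the patients. Knowledge of later symptoms is not documented, and questionnaires were completed online in the feasibility study.
- **That processing starts before any T3 scan exists.** At the stated accrual it is outstanding for roughly 5 to 8 of 44 patients.
- **That a novice reads the trial scans.** The description belongs to the training and reliability stage, before the RCT began. That the student also measures every image is implied, not stated.
- **That bias has been shown.** The thresholds describe vulnerability. Any outcome with n=44 has the same 0.30 SD threshold, and nothing in the documents suggests a reader effect of that size.

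The remedy also has limits. Re-reading saved images cannot remove bias introduced when the scan is taken, and without an untreated group the change over time remains mixed with natural recovery.

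**Conclusion.** The point holds as a gap in stated masking. One examiner, who also screens patients clinically, is masked to allocation and, as far as the plan says, to nothing else. The between-group ultrasound comparison is protected against a shift common to both arms. The within-group changes of Objective 3 and the correlations of Objective 4 are open to reader expectation and, to a minor degree, to drift.

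The size of any actual bias is unknown. The illustrative thresholds (0.30 SD of change at n=44, 0.44 SD in one arm of 22, a correlation of about 0.30) rest on simple one-sample and Pearson tests at a two-sided 0.05 level, not on the planned mixed model. The count of 5 to 8 outstanding T3 scans rests on the accrual rates in the renewal and ignores dropout. The change is worth making because it is cheap; the primary SPADI analysis does not depend on it.

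**What to change.** In Outcome measures (application) and in the RCT data-analysis paragraph of the renewal's second-term plan, state that:

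1. The same examiner measures all stored images after the last T3 scan, with coded file names, all visits in random order, and patient, visit and clinical data hidden.
2. The ultrasound dataset is locked before it is linked to SPADI or to allocation.
3. Values that exist only as live on-screen measurements are flagged.
4. The conclusion for Objective 3 rests on the between-group difference. Within-group change and the Objective 4 correlations are reported as descriptive or exploratory, because masked reading cannot remove acquisition bias or natural recovery.

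**Cost.** No extra patient, scan or staff is needed. Ultrasound measurement starts about five months later (November instead of June 2022), within an analysis period that ends in Q4 2023. File coding and re-measuring take time: up to 44 patients × 4 visits × 7 measures = 1,232 values, before repeats and without allowing for dropout. The procedure depends on saved images, whose availability the documents do not confirm. If they are not available, items 3 and 4 still apply.

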### Updated research approach and work plan for the 2nd term.

Update, elaborate and motivate the planned course of activities for the 2nd term. You might use a table or graphic representation (timing work packages, milestones, critical path).

### WP2 RCT: End of patient recruitment and data collection

As previously mentioned, we changed the timeline compared to the initial FWO proposal, based on the current recruitment rate impacted by the Covid-19 pandemic. The end of patient recruitment will be in May 2022 (**Milestone 2**) and the last follow up will be in November 2022. The adaptations are indicated in dark blue in Table 1. *Status*: data collection.

#### WP3: Data analysis

Data analysis of the RCT (WP3, 3.4 and 3.5): demographics and other objective measures (strength, range of motion, scapular dyskinesis, data from the US machine) will be processed already from June 2022, but the data concerning the randomization process of two groups will be unblinded only at the end of the trial in November 2022. Related manuscripts: see **Manuscript 4 and 5**. The end of the data analysis will be **Milestone 3**. *Status:* Milestone 3 has been delayed from Q2 2022 (initial FWO project) to Q4 2023. This delay is due to a decrease in patient recruitment caused by the pandemic of Covid-19. However, thanks to the extension of the FWO scholarship, there will be sufficient time to recruit all patients and to conduct a thorough data analysis for both objective and subjective measures.

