# WP3: Data analysis

Statistical analyses will be performed using JMP ®Pro 14.0.0 (SAS Institute Inc., Cary, NC, USA) . Level of significance is set at p= 0.05. Appropriate descriptive statistics will be performed.

**OBJECTIVE 1,2,3:** A mixed regression model for repeated measures will be used to assess both the evolution of SPADI (pain and function), strength, ROM and US parameters within persons from baseline (T0) over time (T1, T2, T3) and the differences in evolution between subjects. Potential confounders are: age, gender, BMI, previous corticosteroid injections, severity of initial symptoms. They will be measured during the history taking at the first assessment and added into the mixed regression model as co-variants. If for a certain variable the percentage of missingness will be more than 15%, multiple imputation for missed observation will be used. There are three assumptions for the mixed regression model: change over time, a sensible measure for time (multiple time points of measure), normality of residuals (it will be checked using a Shapiro-Wilk test). If these residuals are not normally distributed, an appropriate transformation will be performed first. Therefore, this model best fits the longitudinal design of the RCT. **OBJECTIVE 4**: correlation analysis between tendon structures and clinical symptoms using the correlation for pairs of continuous variables in JMP.

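### Allocation is released at the end of the trial in November 2022, with no requirement that ultrasound processing, a data lock or the SPADI model be completed first

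*Combined protocol and SAP*

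**What the plan says.** - **Unblinding.** The renewal's WP3 section on analysis of the RCT says that "the data concerning the randomization process of two groups will be unblinded only at the end of the trial in November 2022". The renewal's WP2 section on the end of recruitment says that "the last follow up will be in November 2022".
- **Processing.** The same WP3 section says that demographics, strength, range of motion, scapular dyskinesis and ultrasound data "will be processed already from June 2022". It gives no date by which this must be finished. The end of analysis is set later: "Milestone 3 has been delayed from Q2 2022 (initial FWO project) to Q4 2023".
- **Roles.** The renewal's WP3 section on the ultrasound articles says that "the only US examiner for the RCT is the PhD student". Its WP2 section adds: "The extended time for data analysis in 2023 will allow the PhD student to conduct a thorough data analysis".
- **Masking.** The Outcome measures section says that "the assessors will be blinded to group allocation". Nothing is said about masking the analyst, locking the database or freezing the model.
- **Model.** The original WP3 section names a repeated-measures mixed model, five covariates, multiple imputation above 15% missingness, and a Shapiro-Wilk check of residuals. If that check fails, "an appropriate transformation will be performed first"; which transformation is not said.

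**The concern.** The stated rule ends masking when the trial ends. It does not wait for the work that masking protects. One person acquires the ultrasound measures, processes them and analyses the trial, and from November 2022 that person may know the arms.

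Two things are at stake. Any ultrasound distance or thickness measured or re-measured after that date loses the masking promised under Outcome measures, in a comparison where the investigators expect larger changes in G1 (Objective 3). For the primary outcome, modelling choices that the plan leaves open can be made with the arm contrast in view, in a trial whose stated hypothesis (Objective 1) favours G1.

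**Working it through.** The plan gives no figure to reproduce here. The check is on dates, roles and what the model section settles.

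**1. Last visit against unblinding.** Recruitment ends in May 2022 and T3 is at 26 weeks (182 days).
- 1 May 2022 + 182 days = 30 October 2022.
- 31 May 2022 + 182 days = 29 November 2022.

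The last T3 scans therefore fall at or just before the month of unblinding. The renewal's WP2 section reports 42 recruited by the end of April 2022 against a target of 44, so 44 − 42 = 2 patients are in this position.

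**2. T3 visits within the masked processing window.** A T3 visit on 1 June 2022 corresponds to a baseline on 1 December 2021. The renewal gives 2.6 patients per month in the first year (July 2020 to July 2021, which counts as 12 or 13 months) and 1.2 per month afterwards. Enrolled by the end of November 2021:
- 12 months: 2.6 × 12 + 1.2 × 4 = 36.0, leaving 44 − 36.0 = 8.0.
- 13 months: 2.6 × 13 + 1.2 × 4 = 38.6, leaving 44 − 38.6 = 5.4.

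About 5 to 8 of 44 patients have their T3 visit between June and November 2022. Scans from earlier visits may also be waiting, because processing only starts in June. With four visits each, 44 × 4 = 176 scan visits are planned before dropout. How many will be processed by November is not stated.

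**3. Time from unblinding to the end of analysis.** The shortest span is 30 November 2022 to 1 October 2023, 10.0 months. The longest is 1 November 2022 to 31 December 2023, 14.0 months.

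**4. What the model section fixes and what it leaves open.**
- Fixed: the model family, the five covariates, the 15% trigger for imputation, and the residual check that triggers a transformation.
- Open: which transformation; the covariance structure; how baseline enters (T0 is part of the modelled evolution, while initial severity is also a covariate); the imputation model; and which contrast decides, since Outcome measures lists T1, T2 and T3 without ranking them.
- The imputation model may well be needed. The Sample size section expects 15% dropout. With 44 patients, 6 missing is 6/44 = 13.6% (below the trigger) and 7 missing is 7/44 = 15.9% (above it).

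**5. What late masking can protect, by outcome.**
- SPADI: values come from the patient's questionnaire; only the modelling is exposed.
- Strength and range of motion: taken with a dynamometer and goniometer, apparently recorded at the visit.
- Dyskinesis: visual observation and assistance tests, apparently scored at the visit; no video is mentioned.
- Ultrasound: exposed only if distances or thicknesses are measured, or measured again, from stored images. The documents do not say, although processing of data from the machine suggests some offline work.

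**The case against.** The strongest reply is that the existing rule is already protective. Processing starts in June 2022 while allocation is masked, assessors are promised to be blinded, and unblinding waits for the end of the trial. That stands, and it means unmasked measurement is something the plan permits, not something it intends.

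Four stronger readings are tempting, and the documents do not support them.
- *The ultrasound comparison will be read unmasked.* Offline measurement is not stated, and the dates alone place only the T3 scans of about 2 patients next to unblinding. Those scans would hardly matter. Assume a reader shift of 0.2 SD (not from the documents), both patients in one arm of 22, and a standard error of √(4/44) = 0.30 SD. The mean shift is 0.2 × 2/22 = 0.018 SD, and a two-sided 5% test rejects about 5.04% of the time. A larger effect needs many more scans left unprocessed, which nothing in the plan establishes or rules out.
- *The SPADI false-positive rate is inflated by a known multiple.* Any such figure depends on an invented menu of analyses. Unadjusted change and carry-forward are not options under the plan, because the covariates and the 15% rule are stated. Picking the best of several analyses would also work equally well with arms labelled A and B, so the unblinding date is not its cause.
- *Masking is lost for strength, range of motion and dyskinesis.* These appear to be recorded at the visit.
- *The calendar has no slack.* The rule refers to the end of the trial, so if the last visit slipped, unblinding could be expected to move with it.

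What remains is that no section makes completed processing, a lock or a settled model a condition of release, and that one person holds both roles for about a year afterwards.

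**Conclusion.** The point holds as a gap in sequence. Allocation is released in the month of the last T3 visit, without conditions, to a project in which the sole ultrasound examiner is also the analyst. That person may then measure or re-measure unprocessed scans, and settle the open SPADI modelling choices, knowing the arms.

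Its size cannot be quantified from the documents. It depends on how many scans are processed after unblinding and whether distances are measured offline, and neither is stated. The half that concerns the model does not depend on how scans are read; it rests on the 2023 analysis by the PhD student and the choices listed as open. It does assume that the documents are complete in naming no masked analyst, lock or later frozen plan.

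This is a cheap improvement to a stated rule. It is not evidence that the results will be biased.

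**What to change.** In the renewal's WP3 section, replace the November 2022 trigger with two conditions, both met before allocation is released:

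1. All T0 to T3 ultrasound and other objective values are processed and the dataset is locked.
2. The choices still open (transformation, covariance structure, handling of baseline, imputation model, deciding contrast) are fixed in a dated analysis plan before any between-arm comparison, using pooled data without arm codes.

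The primary SPADI model is then run on arms coded A and B. Coding alone is not enough, because an analyst could still choose among models by their A-versus-B result; the choices must be fixed first. Keep the exercise and pain diaries out of the masked dataset, since pain recorded around training can reveal the arm.

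The cost is a few sentences in the plan and recoding of the arms by whoever holds the randomisation list. No patients or visits are added. The downside is a short delay in unblinding, which the Q4 2023 milestone can absorb.
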